9.0 Participant Remuneration

Study participants will be provided with small values of debit or gift cards for their time and commitment to the study as follows: \$25 at the Baseline, Month 2, Month 4, and Month 6 visits. Participants will also be paid for the cost of parking and transportation for study related activities.

10.0 STATISTICAL CONSIDERATIONS

Data analysis plan: We will use descriptive statistics to characterize the feasibility and process measures listed in Table 5, with 95% confidence intervals. Changes in UFS-QOL scores, the primary outcome, as well as secondary outcomes including hormone levels and fibroid volume, will be compared using linear mixed models for repeated measures, adjusting for baseline. We will estimate 1) between-group differences in change from baseline to months 1 and 2; 2) changes from baseline to months 1-3 and 4-6 in group A; and 3) changes from month 3 to months 5 and 6 within group B.

Sample size calculations: This is a pilot study with the aim of assessing the feasibility of implementing a definitive letrozole trial. Therefore, we chose a sample size that would be large enough to assess feasibility, but small enough to complete the pilot within a the1 year timeframe and with a limited budget. Accordingly, the study will not have power to detect small treatment effects. In the PROMISe pilot study discussed in Preliminary Studies, the standard deviation of the UFS-QOL SSS was 20, and correlation of baseline with follow-up scores declined from 0.5 at 1 month to nearly zero at 3 months. In the analysis for AIM 2 of between-group differences in the change in UFS-QOL from baseline to 2 months , the sample size of 20 will provide 80% power to detect a between-group difference of 13.4 points in average SSS scores at months 1 and 2, after accounting for short term attrition of 10%. In the analysis for AIM 3, assessing longer term changes in SSS scores within group A, the sample of 15 women have 80% power to detect average changes from baseline to months 1-3 and 4-6 of 16.0 points. In additional analysis for AIM 3, assessing changes from month 3 to months 5-6 in group B, the corresponding minimum detectable effect will be 18 points. Effects of this magnitude are

clinically relevant because 15-20 points is the mean difference in SSS between women with symptomatic fibroids and women without fibroids.

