3.0 STUDY OVERVIEW

This is a randomized, blinded, placebo-controlled trial of oral letrozole among 20 premenopausal women with symptomatic uterine fibroids. Participants will be randomly assigned in a 1:1 ratio to either oral letrozole 2.5mg/day for 6 months (Group A) or intermittent dosing with letrozole 2.5mg/day and an identical placebo capsule (Group B). Group B will receive medication dosing as follows: 2 months of placebo, then 2 months daily letrozole 2.5mg/day, then 2 months of placebo (Table 1). This dosing regimen in the two groups will allow for: 1) between group comparisons in month 1 and 2 to assess the efficacy of letrozole compared with a placebo, 2) within-group comparisons in month 3-6 in group B to evaluate the rate of fibroid regrowth after discontinuing letrozole to evaluate the possibility of intermediate dosing and 3) within-group comparisons in group A in month 1-6 to evaluate the safety of long-term letrozole use. This pilot data will be critical for determining the appropriate long-term dosing regimen in a future, larger, full-scale trial of letrozole.

Month	1	2	3	4	5	6
Group A	L	L	L	L	L	L
Group B	P	P	L	L	P	P

We will assess changes in fibroid symptoms, quality of life, and sexual functioning monthly using standardized, validated questionnaires. In addition, at baseline, month 2, 4 and 6, we will assess changes in the following measures:

- 1) fibroid and uterine volume assessed by pelvic ultrasound
- 2) serum follicle stimulating hormone (FSH) and estradiol levels to determine ovarian function

Study participants will be recruited at UCSF. All study data will be stored securely in a HIPAA compliant, secure database monitored by the UC San Francisco Coordinating Center. A data safety and monitoring board will oversee participant safety and protection.

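### Baseline adjustment is not separated from Group A's own change from baseline; if baseline is a covariate there, the interval for that change is too narrow

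*Combined protocol and SAP*

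**What the plan says.** Section 10.0, Data analysis plan, gives one method for the primary outcome (UFS-QOL) and for hormone levels and fibroid volume: changes "will be compared using linear mixed models for repeated measures, adjusting for baseline". The next sentence lists three estimates: the A-versus-B difference in change to months 1 and 2, "changes from baseline to months 1-3 and 4-6 in group A", and Group B's change from month 3 to months 5 and 6. It does not say whether baseline is a covariate or one of the repeated outcomes. It also does not say how a within-group change and its standard error are formed, or which covariance structure or degrees of freedom apply.

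The same section, under Sample size calculations, reports from an earlier pilot that "the standard deviation of the UFS-QOL SSS was 20" and that the "correlation of baseline with follow-up scores declined from 0.5 at 1 month to nearly zero at 3 months". For Group A it states that "the sample of 15 women have 80% power to detect average changes from baseline to months 1-3 and 4-6 of 16.0 points".

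**The concern.** Adjusting for baseline suits the comparison of A with B. Group A's change from baseline is a different quantity, because the baseline mean is itself one of the two things being compared. If baseline is a covariate, the model conditions on the observed baseline values and treats their mean as known. A baseline mean that is high by chance then appears as a precisely estimated improvement. The omitted variance matters most when baseline and follow-up are weakly correlated, which is what the plan reports from month 3.

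Group A's within-group change over months 1-6 belongs to the third primary goal in Section 4.0. Section 2.0 says that the outcome data will supply effect sizes and standard deviations for the next trial. After month 2 Group A has no concurrent placebo group, so its standard error has to stand on its own.

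**Working it through.** **Inputs from the documents.** SD 20; baseline correlation 0.5 at month 1 and near zero at month 3 (Section 10.0); 20 women randomised 1:1, so 10 in Group A, or 9 after the 10% attrition that Section 10.0 uses for its between-group calculation; monthly symptom scores (Section 3.0).

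**Assumptions.** Two-sided alpha 0.05. AR(1) correlation of 0.5, which gives 0.5, 0.25 and 0.125 with baseline at months 1, 2 and 3, and 0.063, 0.031 and 0.016 at months 4, 5 and 6.

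**Notation.** In units of SD squared, *a* is the variance of the average of three follow-up scores and *b* is its mean correlation with baseline.
- Variance of a paired change: 400(a + 1 − 2b)/n.
- Variance reported with baseline as a covariate: 400(a − b²)/n.
- Part left out: 400(1 − b)²/m, where m is the number of women whose baseline mean is the reference (n for Group A alone, 2n for both arms at the overall mean).

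**The plan's own figure first.** For 80% power the detectable change is 2.80 × 20 × √(f/n).
- Setting this to 16.0 with n = 15 gives f = 1.22 by z (1.06 by t).
- A covariate-conditional analysis has f of at most 1.0, so at most 14.5 points by z (about 15.6 by t). Taken at 15 women, the figure therefore counts baseline variability.
- The paired formula at n = 15 gives 14.7-15.6 (z) or 15.8-16.8 (t) for months 1-3, which brackets 16.0.
- For months 4-6 with zero baseline correlation it gives at least 16.7 (z), so 16.0 is not reproduced there.
- At the design's n = 10 the paired formula gives 18.0-22.9 (z). Only the conditional formula comes near 16 (13.9-16.5 by t).

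**Months 4-6, n = 9.** a = (3 + 2(0.5 + 0.5 + 0.25))/9 = 0.611 and b = 0.036.
- Reported SE: 20√(0.610/9) = 5.2.
- True SE, Group A alone: 20√(1.538/9) = 8.3. Ratio 0.63. With t = 2.365 on 7 df, coverage is P(|T₇| < 2.365 × 0.63), about 82%.
- True SE, two-arm model at the overall baseline mean: 20√(0.610/9 + 0.928/18) = 6.9. Ratio 0.75. With t = 2.131 on 15 df, coverage is about 87%.

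**Months 1-3, n = 9.** a = 0.611 and b = 0.292.
- Reported SE: 20√(0.526/9) = 4.8.
- Group A alone: 20√(1.028/9) = 6.8. Ratio 0.72, coverage about 86-87%.
- Two-arm: 20√(0.526/9 + 0.502/18) = 5.9. Ratio 0.82, coverage about 90%.

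**Simulation.** Trials simulated with no true change under the same assumptions agree:

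| | Group A alone | Two-arm | Paired change |
|---|---|---|---|
| Months 4-6 | 82% | 87-88% | 95% |
| Months 1-3 | 86-87% | 90% | 95% |

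**Sensitivity at months 4-6, n = 10.**
- Baseline correlation 0 and equal follow-up correlations of 0.5-0.9: coverage is 82-85% (Group A alone), 80-84% (two-arm at Group A's own mean) and 87-90% (two-arm at the overall mean).
- Baseline correlation 0.2: 84-91% across the same choices.
- Uncorrelated follow-up scores with z critical values: as low as 64%.

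**Interval width.** With n = 10, baseline correlation 0 and follow-up correlation 0.5, the paired half-width is 2.262 × 20√(1.667/10) = 18.5 points. With the baseline mean treated as fixed it is 2.306 × 20√(0.667/10) = 11.9 points.

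**Outcomes that track baseline closely.** For a single follow-up value with correlation ρ, the SE ratio is √((1 + ρ)/2): 0.95 at ρ = 0.8 and 0.99 at ρ = 0.95. A volume measure in that assumed range would have an SE only 1-5% too small.

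**The case against.** The strongest reply is that the plan does not prescribe the faulty analysis. Adjusting for baseline is attached to comparing, the estimates come in a separate sentence, and the third estimate starts from month 3, which must itself be an outcome. The 16.0 points at 15 women also need a variance that includes baseline. This stands as a reason to word the point conditionally. It does not remove it: no other method is written for Group A's change, and the covariate is the usual meaning. The power figure is not decisive, because Group A has 10 women rather than 15, and at 10 only a conditional formula comes near 16. That mismatch is a separate matter.

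A reader might infer that the trial's 95% intervals for symptom change, or its 5% tests, are certain to fail. The documents do not support that. Section 10.0 promises to "characterize the feasibility and process measures listed in Table 5, with 95% confidence intervals" but says nothing of the kind for symptom change, and it states no alpha or decision rule. A false-positive rate of 12-18% at months 4-6 (100 minus 88 and 82) would follow only if a 5% test were built on this standard error.

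Lower coverage, near 80%, can be obtained from a random-intercept model with z critical values. Under AR(1) data, however, that model already covers only 91.6% at months 4-6 when the baseline is known, so part of the shortfall has other causes.

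Finally, this is a feasibility pilot and no efficacy decision rests on the Group A interval. That lowers the priority of the correction but does not make the standard error right.

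**Conclusion.** The point holds in conditional form. If baseline enters as a covariate for Group A's own change, the standard error is too small, and a nominal 95% interval for the symptom score covers about 82-88% at months 4-6 and 86-90% at months 1-3. These figures rest on SD 20, AR(1) correlation of 0.5, 9 to 10 women per arm and t-based intervals. The correlation among follow-up scores is not in the documents; it changes the size of the shortfall but not its direction. It would be wrong to extend the point to the placebo-controlled comparison in months 1 and 2, which is unaffected, or to give it weight for outcomes highly correlated with baseline. For a 20-woman pilot this should be fixed but does not threaten the study. Confidence is moderate, because the covariate reading is natural rather than explicit.

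**What to change.** State in Section 10.0 that the baseline covariate applies to the between-group contrast only. For Group A's change, specify one of two methods:

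- each woman's paired change (mean of months 1-3, or of months 4-6, minus baseline) with a t-based interval; or
- a mixed model with month 0 as one of the repeated outcomes, no baseline covariate, a covariance that is unstructured or decays with time, and small-sample degrees of freedom.

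A random intercept alone is not enough in the second option: with baseline as an outcome it gave coverage of only 71-93% in simulation. Paired change, or month 0 as an outcome with unstructured covariance, gave about 95%. A particular decaying structure or degrees-of-freedom method is a matter of choice.

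The cost is a sentence or two of wording and no new data. The downside is wider Group A intervals, for example about 18.5 rather than 11.9 points either side in the n = 10 case above.

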2.0 STUDY RATIONALE

Although there is preliminary evidence to demonstrate a positive effect of AIs on reducing fibroid volume, current studies are insufficient to support widespread clinical use. There are only 2 trials of letrozole monotherapy for fibroids with a total of 56 women; both are open-label, unblinded studies. A randomized, blinded, placebo-controlled trial is needed for an unbiased assessment of letrozole efficacy. In addition, most women with symptomatic fibroids are 35-50 years old and may require many years of treatment until menopause when fibroids regress spontaneously with falling serum estrogen levels. All current AI studies are short-term with only 2-3 months of drug delivery due to lingering concerns that AIs might induce hypoestrogenism among premenopausal women. There are also no studies that evaluate the rate of fibroid regrowth after stopping AIs when fibroid estrogen levels may rapidly rise. If fibroids regrow slowly over several months after stopping AIs, there may be a role for intermittent AI dosing to maximize benefit and minimize harm. Studies are needed to assess the safety profile of letrozole for >3 months of use and to evaluate changes in fibroid volume after letrozole is discontinued.

Our ultimate goal is to conduct a multi-centered, randomized, trial of letrozole versus placebo among women with symptomatic fibroids. This trial will provide gold standard evidence to determine if letrozole results in symptom improvement but offers the advantages of less morbidity and lower rates of recurrence of fibroid symptoms.

To prepare for a future multi-centered randomized trial of letrozole, we will first conduct a controlled pilot study (the PLUM study). The pilot will allow us to assess the feasibility of recruiting and retaining study participants to this drug intervention trial. We will also complete essential preparatory work for a future randomized trial; we will create and test study forms, a manual of operations, and a study database that can be easily adapted for a multi-site trial. The PLUM pilot study will lay the foundation for a successful future study of letrozole as a treatment for uterine fibroids.

The PLUM study will also provide preliminary data on the efficacy of letrozole in treating uterine fibroids. We will use PLUM outcome data to estimate effect sizes and standard deviations to calculate an appropriate sample size for a future randomized trial.

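### Group B's regrowth contrast starts at month 3, but letrozole stops at the end of month 4: volume and hormones have no starting value, and for symptoms the contrast mixes on-drug with off-drug change

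*Combined protocol and SAP*

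**What the plan says.** Table 1 in Section 3.0 gives Group B placebo in months 1-2, letrozole in months 3-4 and placebo in months 5-6. Sections 3.0 and 4.0 both say that the Group B within-group analysis is there to show how fast fibroids regrow once letrozole stops. Section 2.0 says studies are needed "to evaluate changes in fibroid volume after letrozole is discontinued", and links a possible role for intermittent dosing to slow regrowth.

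The data analysis plan in Section 10.0 says that UFS-QOL (the primary outcome) and "secondary outcomes including hormone levels and fibroid volume" "will be compared using linear mixed models for repeated measures, adjusting for baseline". It then lists three contrasts for all of these outcomes. The third is "changes from month 3 to months 5 and 6 within group B". The sample size paragraph repeats the same start month: "assessing changes from month 3 to months 5-6 in group B, the corresponding minimum detectable effect will be 18 points".

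The measurement schedule differs by outcome. Symptoms are frequent: "We will assess changes in fibroid symptoms, quality of life, and sexual functioning monthly". Ultrasound (6.1.B) and estradiol and FSH (6.1.C) are taken at baseline and the end of months 2, 4 and 6 only. Table 2 in 6.1.G agrees.

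**The concern.** A contrast meant to show change after stopping should start at the last on-drug measurement. For Group B that is the end of month 4. The plan names month 3 instead, with two consequences.

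- **Volume and hormones.** No woman has a scan or blood draw scheduled at month 3 or month 5, so the analysis as written has no starting value. Someone would have to choose one later, possibly with the data in hand, and the candidates give very different answers.
- **Symptoms.** The SSS contrast can be computed but it estimates a mixture of two periods, one on drug and one off.

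This is the only contrast in Section 10.0 aimed at regrowth, and Section 3.0 treats the pilot data as critical to choosing the regimen for the larger trial.

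**Working it through.** **1. Contrasts set against the schedule (volume and hormones: baseline, months 2, 4, 6)**

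- Contrast 1, baseline to months 1 and 2: month 1 is not measured, but baseline to month 2 is a usable pair.
- Contrast 2, Group A, baseline to months 1-3 and 4-6: months 1, 3 and 5 are not measured, but baseline to months 2, 4 and 6 are usable pairs.
- Contrast 3, Group B, month 3 to months 5 and 6: only month 6 is measured. There is no starting value and so no usable pair.

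A repeated-measures mixed model does not fill this gap. It cannot estimate a mean at a visit nobody attends unless a time trend is imposed, and none is specified.

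**2. How much the choice of starting value matters for volume**

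This is an illustration, with month 2 = 100. Assumptions: no change on placebo, and Group B follows the course in Section 1.0 (45-46% shrinkage at 3 months, 90% of it within 1 month).

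- Month 3 = 100 − 0.9 × 45 = 59.5, or 100 − 0.9 × 46 = 58.6.
- Month 4 lies between the 1-month and 3-month values: 54 to 59.5.
- A month-3 value interpolated from the two neighbouring scans = (100 + month 4)/2 = 77 to 79.75. Pairing each course with its own month 4, that is 18.0 to 20.7 points too high.
- If regrowth took 2-3 months at a constant rate (the time Section 1.0 gives for GnRH agonists, assumed here for letrozole), the month 4 to 6 change would be between 2/3 × 40.5 = +27 and +46. With no regrowth it would be 0.

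Take month 4 = 59.5 and regrowth of 27, so month 6 = 86.5. The change to month 6 is then +27 from month 4, 86.5 − 79.75 = +6.75 from an interpolated month 3, and 86.5 − 100 = −13.5 from month 2. One set of data gives three different answers.

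**3. What the SSS contrast contains**

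mean(M5, M6) − M3 = (M4 − M3) + [mean(M5, M6) − M4]

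The first term is on drug and the second is the change wanted. If SSS followed the volume course (assumed), at most 10% of the response would fall after the first month on drug, which is 0 to 2 points for a response of up to 20. A further improvement of 2 points in month 4 followed by a worsening of 10 would show as 8.

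**4. The stated detectable effect of 18 points**

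Inputs from Section 10.0: SD 20, 80% power, and "correlation of baseline with follow-up scores declined from 0.5 at 1 month to nearly zero at 3 months". Assumed: two-sided 5%; the correlations apply between any two months with r1 = 0.5, r2 = 0.25 (not given) and r3 = 0; months 5 and 6 are averaged. Normal-approximation MDE = 2.80 × SD/√n.

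- Month-3 start: variance = 400 × (1.5 + 0.5·r1 − r2 − r3) = 400 × 1.5 = 600, SD 24.5. With n = 15, the figure the plan uses for Group A, MDE = 17.7 (paired t 19.1), close to the stated 18. With the 10 women that 20 randomised 1:1 gives, MDE = 21.7 (paired t 24.4).
- Month-4 start: variance = 400 × (1.5 − 0.5·r1 − r2) = 400 × 1.0 = 400, SD 20.0. With n = 10, MDE = 17.7 (paired t 19.9). For r2 from 0 to 0.5 the range is 19.8 to 15.3 (paired t 22.3 to 17.3).
- Expected 95% CI half-width, month-4 start, n = 10: t(0.975, 9) × 20.0/√10 = 14.3 points (16.0 to 12.4 over the same range of r2).
- With 9 or 8 completers (assumed), the month-4 MDE is 18.7 or 19.8 (paired t 21.3 or 23.1).

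Month 3 with n = 15 and month 4 with n = 10 both give 17.7, so the stated 18 does not reveal which start was intended. No MDE can be computed for volume or hormones, because the documents give no SD for either.

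**The case against.** The strongest reply is that this is a labelling slip. Given the stated purpose and the scan dates, only month 4 to month 6 makes sense for volume, and an analyst would use it. The month lists suit the monthly primary outcome, and the other two contrasts also name months without scans. It is true that no data are lost and that month 4 to 6 is the sensible reading. But the text names month 3 twice, and contrast 3 differs from the others in having no measured start.

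A second reply is that the SSS distortion is trivial: 0 to 2 points against a CI half-width of 14.3. That stands as far as the volume analogy holds, and the symptom part alone would be minor. The documents give no symptom course for month 4, so neither the size nor the direction is known.

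A third is that interpolation is not planned, so its error is hypothetical. That is correct. The figure shows only why the model cannot be relied on to supply the missing value.

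Reading month 3 as the month 2 visit, that is, the start of month 3, does not rescue the contrast. That value precedes letrozole, so the contrast would show net residual effect and not regrowth.

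Finally, a month 4 to 6 change does not by itself give the fraction of shrinkage regained; that also needs Group B's month 2 to 4 change. This is a fair suggestion for an addition, but the correction is sound without it.

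**Conclusion.** The concern holds. Contrast 3 cannot be computed as written for fibroid volume, estradiol or FSH, and for SSS it does not isolate the change after stopping. Both conclusions follow from the dosing table and visit schedule alone and do not depend on any power assumption.

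The sizes do rest on assumptions. The volume figures borrow the Section 1.0 shrinkage course and the GnRH regrowth time. The SSS contamination of 0 to 2 points assumes that symptoms track volume. The detectable effects assume a two-sided 5% test, an unstated two-month correlation and averaging of months 5 and 6.

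The point should be fixed, in proportion: this is an uncontrolled contrast in about 10 women, in a pilot with no decision rule attached, and the randomised month 1-2 comparison is untouched.

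**What to change.** In Section 10.0, define month k as the end of month k and replace contrast 3 with wording such as: within Group B, change from month 4 to month 6 in fibroid and uterine volume, estradiol and FSH, and from month 4 to months 5 and 6 in UFS-QOL SSS, each with a 95% CI.

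Restate the SSS detectable effect for the month-4 start, giving Group B's n (10 at 1:1), alpha and the correlations used. Label any attrition applied to months 4-6 as an assumption: the plan's figure, "after accounting for short term attrition of 10" percent, is given only for the month 1-2 comparison. If the fraction regained is of interest, Group B's month 2 to month 4 change can be added from scans already scheduled.

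The cost is plan wording and one restated power figure. No visit, procedure or treatment changes. The remaining limitation is that volume yields a single two-month change after stopping, not a regrowth curve.

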4.0 STUDY OBJECTIVES

The PLUM study will collect essential preliminary data to guide and inform a future multi-centered, randomized trial of letrozole versus placebo. The 3 primary study goals are:

1. To assess the feasibility of conducting a randomized, placebo-controlled trial of letrozole for premenopausal women with fibroids.
2. To collect pilot data that examines differences in fibroid symptoms, fibroid volume, and hormone levels among premenopausal women who take letrozole compared with a placebo.

These will be between-group analyses in Months 1 and 2 (Group A vs. Group B) that serve as preliminary data on the efficacy of letrozole in a placebo-controlled trial.

3. To collect pilot data that examines changes in fibroid symptoms, fibroid volume, and hormone levels among premenopausal women taking continuous and intermittent letrozole dosing.

These will be within-group analyses as follows: Months 1-6 for Group A, Months 3-6 for Group B. These data will provide preliminary information on the safety of letrozole use beyond 3 months (Group A) and the rate of fibroid regrowth after letrozole is discontinued (Group B).

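### Twenty women randomised 1:1 do not give 80% power for a 13.4-point SSS difference (about 16 to 25 points is detectable under plausible correlations), and the group A figure assumes 15 women where at most 10 exist

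*Combined protocol and SAP*

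**What the plan says.** Section 3.0 sets the design: 20 women, and "Participants will be randomly assigned in a 1:1 ratio" to continuous letrozole (group A) or to placebo, letrozole, placebo (group B). Each group therefore has 10 women.

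Section 10.0 makes three statements about detectable differences in the UFS-QOL symptom severity score (SSS):

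- Aim 2, between groups at months 1 and 2: "the sample size of 20 will provide 80% power to detect a between-group difference of 13.4 points in average SSS scores", with 10% short-term attrition taken into account.
- Aim 3, within group A: "the sample of 15 women have 80% power to detect average changes from baseline to months 1-3 and 4-6 of 16.0 points".
- Aim 3, within group B from month 3 to months 5 and 6: "the corresponding minimum detectable effect will be 18 points", with no n given.

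The stated inputs are that "the standard deviation of the UFS-QOL SSS was 20, and correlation of baseline with follow-up scores declined from 0.5 at 1 month", falling to almost zero by 3 months, and that the analysis is a linear mixed model adjusted for baseline. The effects are called clinically relevant because "15-20 points is the mean difference in SSS between women with symptomatic fibroids and women without fibroids". The section also says that N was chosen for feasibility and that small effects are out of reach.

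**The concern.** With an SD of 20 and 9 women per arm, 13.4 points is a small difference to detect with 80% power, even after averaging two visits and adjusting for baseline. The group A sample of 15 cannot come from 20 women split equally. Together these suggest that the calculations were not done for the design described.

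UFS-QOL is the primary outcome, and this is the only between-group power statement. Section 4.0 says the month 1 and 2 comparisons "serve as preliminary data on the efficacy of letrozole in a placebo-controlled trial". The stated 13.4 points lies below the 15 to 20 point benchmark, so a reader would conclude that the pilot can detect clinically relevant differences. If the true detectable difference is above 20 points, that reassurance is wrong, and a null comparison could be over-read.

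**Working it through.** **Inputs from the plan.** N = 20 and 1:1 allocation (section 3.0). From section 10.0: 10% attrition, SD 20, baseline correlation r1 = 0.5 at month 1 and near zero at month 3, baseline adjustment, 80% power. Analysed: 20 × 0.9 = 18, or n = 9 per arm.

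**Inputs the plan does not give, with the range used.** Alpha: two-sided 0.05. Month-2 baseline correlation r2: 0 to 0.5, with 0.25 as the interpolated central value. Correlation ρ between months 1 and 2: 0.25 to 0.7, central 0.5. The lower limit of 0.25 is what two visits would show if they were related only through a baseline that each correlates with at 0.5 (0.5 × 0.5).

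**Formulas.** For the baseline-adjusted mean of two visits, SD_eff = 20 × √[(1 + ρ)/2 − r̄²], with r̄ = (r1 + r2)/2. Detectable difference = (1.960 + 0.842) × SD_eff × √(2/n). The t version uses the noncentral t on 2n − 3 = 15 df.

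**Attempt to reproduce 13.4.** At n = 9 it needs SD_eff = 13.4 / (2.802 × √(2/9)) = 10.1. The smallest SD_eff in the range above is 12.2. The figure is not reproduced.

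**Central case (r2 = 0.25, ρ = 0.5).** SD_eff = 20 × √(0.75 − 0.375²) = 15.6. Standard error = 15.6 × √(2/9) = 7.36. Detectable difference = 2.802 × 7.36 = 20.6 points (t: 22.1). Power at 13.4 = Φ(13.4/7.36 − 1.96) = 45% (t: 40%).

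**Full range, n = 9 per arm:**

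| r2 | ρ | Detectable, normal / t | Power at 13.4, normal / t |
|---|---|---|---|
| 0.5 | 0.25 | 16.2 / 17.3 | 64% / 58% |
| 0.5 | 0.5 | 18.7 / 20.0 | 52% / 47% |
| 0.5 | 0.7 | 20.5 / 21.9 | 45% / 40% |
| 0.25 | 0.25 | 18.4 / 19.7 | 53% / 48% |
| 0.25 | 0.5 | 20.6 / 22.1 | 45% / 40% |
| 0.25 | 0.7 | 22.2 / 23.8 | 39% / 35% |
| 0 | 0.25 | 19.8 / 21.2 | 47% / 43% |
| 0 | 0.5 | 21.9 / 23.4 | 40% / 36% |
| 0 | 0.7 | 23.4 / 25.1 | 36% / 32% |

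The 95% confidence interval half-width (t, 15 df) is 12.3 to 17.8 points, centrally 2.131 × 7.36 = 15.7. For 80% power at 13.4 points, 14 to 28 analysed women per arm are needed (normal) or 15 to 29 (t).

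**A possible origin.** With 20 women per arm less 10%, n = 18 gives 13.2 / 13.6 when all correlations are 0.5, and 13.0 / 13.4 when r2 = ρ = 0.25. At the central inputs it gives 14.6 / 15.0. So 20 may have been used as the per-arm size, but the documents do not show this, and the conclusion does not rest on it.

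**Group A.** Taking 16.0 as correct at n = 15, the implied SD of change is 16.0 × √15 / 2.802 = 22.1 (t: 20.6). At n = 10 the detectable change becomes 16.0 × √(15/10) = 19.6 points (t: 20.5), and power at 16.0 is 63% (t: 59%). At n = 9 it is 20.7 (t: 21.9).

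A direct calculation is also possible. For change to a three-visit mean, SD = 20 × √[1 + (1 + 2ρ)/3 − 2r]. With the near-zero baseline correlation reported by month 3 (r = 0) and ρ = 0.5, SD = 25.8, and 10 women give 2.802 × 25.8 / √10 = 22.9 points for months 4 to 6.

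**Group B.** If 18 points was also computed for 15 women (an assumption), 10 women give 18 × √(15/10) = 22.0 points (t: 23.0).

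**The case against.** The strongest objection is that the 16 to 25 point range depends on three inputs the plan omits, so favourable choices might recover 13.4. Some come close:

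- Nine per arm with r2 = 0.5 and ρ = 0 gives 13.2 (t: 14.1). This needs two visits that each correlate 0.5 with baseline but not at all with each other, and it ignores the stated fall in correlation. With r2 = 0.25 and ρ = 0 the result is 15.8 (t: 16.9).
- One-sided 0.05 with 9 per arm gives 14.4 or more over the range (normal).
- Ten per arm with no attrition gives 15.3 or more (normal).
- Combining 10 per arm, one-sided 0.05 and the most favourable correlations gives 13.6 (normal). This drops the attrition that the plan says it included, and still falls short.

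None of these is an ordinary reading of section 10.0.

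The group A replacement is less secure. It is back-solved from 16.0, and the documents do not show whether the 15 or the 16.0 is the slip. With all correlations at 0.5, 10 women would give 14.5 points (t: 16.3), close to the stated value. That requires a baseline correlation of 0.5 throughout, against the plan's own near-zero value by month 3. The sponsor should recompute from its actual inputs rather than adopt 19.6 to 20.5.

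It is also fair that this is a feasibility pilot, that no decision rule depends on 13.4, and that the plan nowhere says a null result would count against letrozole. Section 2.0 says "We will use PLUM outcome data to estimate effect sizes and standard deviations to calculate an appropriate sample size", and a wrong planning figure does not alter those observed values. This limits the consequence. The disclaimer about small effects, however, does not correct a specific claim of 80% power.

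**Conclusion.** Both parts hold. A group A sample of 15 contradicts 20 women randomised 1:1, whatever else is assumed. The claim of 80% power at 13.4 points does not follow from the plan's SD, attrition and baseline correlations. Power there is roughly one-third to two-thirds, and the central detectable difference is about 21 to 22 points, above the 15 to 20 point benchmark instead of below it. The size of the shortfall depends on the assumed alpha, month-2 correlation and between-visit correlation. That there is a shortfall does not, within any plausible choice of them. The group A figure of 16.0 and the group B figure of 18 have no valid stated sample size behind them. The figures should be corrected, but N = 20 remains defensible on feasibility grounds.

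**What to change.** Keep N = 20 and revise the sample size paragraph of section 10.0:

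1. Replace 13.4 with the value for 9 analysed women per arm, recomputed from the sponsor's actual inputs. It is about 21 to 22 points at baseline correlations of 0.5 and 0.25 and a between-visit correlation of 0.5.
2. State the alpha, sidedness, month-2 baseline correlation and between-visit correlation used.
3. Correct the sample of 15, and recompute the group A and group B figures for at most 10 women per group, giving n and attrition for each.
4. Qualify the clinical-relevance sentence: differences within or below 15 to 20 points may be missed.

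Two additions are good practice, not corrections. One is to give the expected 95% confidence interval half-width (about 12 to 18 points, centrally 15 to 16) as what the pilot can deliver. The other is to say that a null month 1 and 2 comparison is not evidence against letrozole.

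The cost is wording only. Sample size, design and analysis are unchanged, but the stated detectable effects are likely to become less favourable.
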